Any measure needs to be robust enough to handle a variety of glucose monitoring patterns used in day-to-day diabetes practice, intuitive in that it measured glucose swings, mathematically rigorous and finally easy to use. A newer measure of lability based on the change in glucose over time has been the Lability Index (LI) . A typical range for a diabetes population was calculated in 100 subjects with T1D who were not selected because of any particular problems. Most subjects have scores under 300 mmol/L/h wk with a median of 223 (25 - 75th percentiles 130 - 329 mmol/L/h wk). An LI  $\geq 433$  mmol/L/h wk (90th percentile) indicated serious problems with glycaemic lability. The LI correlated well with a

clinical scoring of lability by diabetologists and showed improvement after successful islet transplantation and rose when graft function was lost.

The LI has proven useful in the assessment of subjects being considered for an islet transplant. Many patients have been referred with labile diabetes based on the subjective impressions of their caregivers. The LI helps place the difficulty of their glucose control in perspective. The LI has also been useful in the follow-up of subjects after transplantation. The LI after the first transplant improved dramatically once endogenous insulin was provided to smooth insulin delivery and with insulin independence, the LI was superb. It should be clear that the LI is simply a measure of the glucose lability and not an indication for an islet transplant. Rather it indicates that there is a problem and islet transplantation is only an option when other avenues of diabetes management have been exhausted.

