### 1.4.2 Immunosuppressive Medications

In this trial, we hypothesize that avoidance of the diabetogenic drug, tacrolimus and complete avoidance of the anti-angiogenic drug, sirolimus will create a more favorable environment for islet engraftment and function, and will thus substantially improve the rate of success with single donor transplants and minimize or avoid non-immune toxicities such as hypertension, hyperlipidemia, and nephrotoxicity. The trial is a two-center, prospective pilot study of islet transplantation using a steroid-free, calcineurin-inhibitor-free belatacept-based immunosuppressive medication in 20 subjects with long-standing T1D that is refractory to intensive insulin therapy that meet all additional entry criteria and has given informed consent.

The study medication, belatacept, will be administered using the modified less intensive regimen that was derived from the phase 2 human renal transplant trial and is consistent with the less intensive dosing regimen used in the phase III program. Based on results from the

completed phase 2 study, both the less intensive and more intensive regimens appear acceptable. Both regimens met the primary endpoint of non-inferiority to CsA in acute rejection. Both exhibited subject/graft survival similar to CsA, improved GFR, and a lower incidence of CAN. The less intensive dosing regimen will be augmented with a dose at Day 4 to ensure adequate immunosuppression in the early, immunologically-critical, period. Based on this information we will employ the modified lower intensity regimen when testing belatacept. This should result in achieving target levels consistently without excessive immunosuppression.

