#### 4.1.2.1 SECONDARY EFFICACY ENDPOINTS

At  $75 \pm 5$  days following the first islet transplant and following each subsequent islet transplant:

- The percent reduction in insulin requirements
- HbA1c
- Mean amplitude of glycemic excursions (MAGE)
- Glycemic lability index (LI)
- Ryan hypoglycemia severity (HYPO) score
- Basal (fasting) and 90-min glucose and c-peptide derived from the mixed-meal tolerance test (MMTT)
- $\beta$ -score
- C-peptide: (glucose X creatinine) ratio
- Acute insulin response to glucose (AIRglu), insulin sensitivity, and disposition index (DI) derived from the insulin-modified frequently-sampled IV glucose tolerance (FSIGT) test
- Glucose variability and hypoglycemia duration derived from the continuous glucose monitoring system® (CGMS)
- Quality of life (QOL) measures

If a third transplant occurs less than 75 days after the second transplant, the 75 day endpoint data for the second transplant will not be collected.

At  $365 \pm 14$  days following the first and final islet transplant:

- The percent reduction in insulin requirements
- HbA1c
- MAGE
- LI
- Clarke score
- HYPO score
- Basal (fasting) and 90-min glucose and c-peptide (MMTT)

- $\beta$ -score
- C-peptide: (glucose X creatinine) ratio
- AIRglu insulin sensitivity, and disposition index (DI) derived from the FSIGT test
- Glucose variability and hypoglycemia duration derived from the continuous glucose monitoring system® (CGMS)
- QOL measures
- The proportion of subjects receiving a second islet transplant
- The proportion of subjects receiving a third islet transplant
- Rate of favorable outcome at each center preparing islets (rate of subjects with an HbA1c < 7.0% and free of severe hypoglycemic events)

Secondary efficacy endpoints measured at  $365 \pm 14$  days following the final islet transplant will include the change in the above measures from the results obtained at  $75 \pm 5$  days following the final islet transplant.

At two years (730+14 days) following the final islet transplant:

- The percent change from baseline insulin requirements
- The number of severe hypoglycemic events from 28 days to two years
- HbA1c
- Clarke score
- Basal (fasting) and 90-min glucose and c-peptide (MMTT)
- $\beta$ -score
- C-peptide: (glucose • creatinine) ratio
- CGMS
- QOL

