#### **10.2.2 Secondary Endpoints**

Secondary endpoints are defined in section 4.1.2. There are a very large number of secondary endpoints so there will be no adjustment for multiplicity. We will not impute values for secondary endpoints but will conduct a sensitivity analysis to determine the potential magnitude of the contributions of the missing values. Details of the sensitivity analysis will be included in the SAP.

Analysis of secondary endpoints will use methods similar to those defined for the primary outcome. When the endpoint is a proportion such as patients achieving insulin independence at one year after completing their first islet transplant then the observed rate will be used as the point estimate and an exact 95% binomial confidence interval will be reported. Continuous variables will be treated in a similar fashion. If the necessary normality assumption is valid then the sample mean will be used as the point estimate and the usual 95% normal confidence intervals will be computed. Where the normality assumptions are not valid and an appropriate transform will achieve normality then the inverse of the mean of the transformed data will be used as the point estimate and the inverse of the endpoints for a standard 95% confidence interval for the transformed mean will be reported for the confidence interval. If no valid

transformation can be found then we will use the bootstrap method to construct a point estimate and a 95% confidence interval.

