## 10.4 Sample Size and Power Calculations

The purpose of this pilot study is to estimate the true rate of insulin independence at 75 days. The selected sample size is 10 subjects. The point estimate of the true insulin independence rate will be the proportion of the 10 patients that achieve insulin independence. The precision of the estimate depends on the observed number of subjects achieving insulin independence. The following table displays the confidence intervals that would be computed for each possible outcome. If 5 of the 10 subjects achieve insulin independence then the estimated rate will be 50% and a 95% confidence interval will be 0.1871 to 0.8129. That is, we are 95% confident that the true rate is at least 18.71% and no more than 81.29%. The confidence interval rules out any rate less than 18.71% or greater than 81.29%. If 3 patients (30%) achieve insulin independence, then the confidence interval will rule out any rate less than 6.67% or greater than 65.25%.

*Table 5: Confidence Intervals for each possible outcomes*

Number of Subjects insulin Independent at 75 Days	Estimated Rate	Exact 95% Confidence Interval	
		Lower Bound	Upper Bound
0	0	0	0.3085
1	0.1	0.0025	0.445
2	0.2	0.0252	0.5561
3	0.3	0.0667	0.6525
4	0.4	0.1216	0.7376
5	0.5	0.1871	0.8129
6	0.6	0.2624	0.8784
7	0.7	0.3475	0.9333
8	0.8	0.4439	0.9748
9	0.9	0.555	0.9975
10	1	0.6915	1

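### Section 10.2.2 lets a normality judgement on 10 or fewer values decide which quantity is reported for each continuous secondary endpoint, and does not hold that choice fixed across visits

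*Protocol*

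**What the plan says.** Section 10.2.2 gives a three-way rule for continuous secondary endpoints.

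- **Normality accepted:** "If the necessary normality assumption is valid then the sample mean will be used as the point estimate", with a normal 95% interval.
- **Normality not accepted, but a transform works:** "the inverse of the mean of the transformed data will be used as the point estimate", with back-transformed interval limits.
- **No transform works:** "then we will use the bootstrap method to construct a point estimate and a 95% confidence interval". The parameter is not named.

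The section gives no criterion for normality and names no transform. It does not say whether the decision is made once per endpoint or afresh at each visit.

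On numbers, Section 10.4 states "The selected sample size is 10 subjects", and Section 10.2.2 adds "We will not impute values for secondary endpoints". Appendix 1 stops the metabolic tests after graft failure, so a later visit can have fewer values than an earlier one. Section 4.1.2.1 lists largely the same measures at Day 75 and Day 365, after the first and the final transplant. For Day 365 after the final transplant it adds that the endpoints "will include the change in the above measures from the results obtained at" Day 75.

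**The concern.** The arithmetic mean and a back-transformed mean do not estimate the same thing. If the transform is the logarithm, the back-transformed mean is a geometric mean, which for skewed data lies near the median and below the mean. A rule that picks between them from the data makes the target of estimation depend on the sample. With 10 or fewer values a normality check has little power, so for a moderately skewed measure the choice is largely chance.

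A reader will compare the Day 75 and Day 365 tables, or the after-first and after-final tables. If one entry is a mean and the other a geometric mean, part of the difference is only the change of estimator. The confidence intervals do not cover that part, because each is an interval for its own parameter. The secondary results carry weight: Section 10.2.1 judges whether further study is warranted in the light of all of them. With a single arm, no concurrent group would show the artefact.

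**Working it through.** **The plan's own figure.** Table 5 in Section 10.4 covers only the binary primary endpoint. All 11 exact intervals reproduce to four decimals (5 of 10 gives 0.1871 to 0.8129). The protocol gives no figure for continuous endpoints.

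**Inputs from the protocol.** n is at most 10 (Section 10.4), there is no imputation, and the three branches are as in Section 10.2.2.

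**Assumptions, none of them in the protocol.** Values are lognormal with log-scale SD s. Day 75 and Day 365 have the same distribution, so there is no true change. The check is Shapiro-Wilk at 5%, applied at each visit. The transform is the logarithm. Correlation between visits on the log scale is 0 or 0.5.

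**Formulas.** Arithmetic over geometric population mean = exp(s²/2). With rejection probability p and independent visits, P(different branches) = 2p(1 − p). For s = 0.5: exp(0.125) = 1.13, p = 0.25, and 2 × 0.25 × 0.75 = 0.375. Correlated visits and apparent changes come from simulation, with several thousand pairs per case.

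| s (n = 10) | mean / geometric mean | check rejects | visits in different branches | median apparent fall, mean to geometric mean |
|---|---|---|---|---|
| 0.3 | 1.05 | 12% | 20–22% | about 3–4% |
| 0.5 | 1.13 | 25% | 34–38% | about 9–11% |
| 0.75 | 1.32 | 43–44% | 46–50% | about 18–21% |
| 0.8 | 1.38 | 47% | 46–50% | about 19–21% |

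About half of the switches go from mean to geometric mean and give the falls shown. The other half go the other way and show rises (22–24% at s = 0.75). At n = 6 the check rejects less often, and the branches differ in 21–22% of cases at s = 0.5 and 32–33% at 0.75.

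**Evidence on skewness in the protocol.** Section 1.3.1 gives the lability index (LI) in an unselected reference group "with a median of 223 (25 - 75th percentiles 130 - 329", with a 90th percentile of 433.

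- The quartiles lie 223 − 130 = 93 and 329 − 223 = 106 from the median, which is nearly symmetric.
- A normal curve with SD (329 − 130)/1.349 = 147.5 predicts a 90th percentile of 223 + 1.2816 × 147.5 = 412, or 419 if centred on the quartile midpoint 229.5.
- A lognormal with log-SD ln(329/130)/1.349 = 0.69 predicts 223 × exp(1.2816 × 0.69), about 539.

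The stated 433 is close to the normal prediction.

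**Median intervals for the fix.** Coverage of the r-th to q-th ordered value is P(r ≤ B ≤ q − 1) with B ~ Binomial(n, 0.5).

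- n = 10, 2nd to 9th: 1 − 22/1024 = 97.9%.
- n = 9, 2nd to 8th: 1 − 20/512 = 96.1%.
- n = 6, minimum to maximum: 1 − 2/64 = 96.9%.
- n = 5, minimum to maximum: 1 − 2/32 = 93.75%, below 95%.

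**The case against.** Section 10.1 leaves analysis details to the SAP, which is not at hand. The SAP may name the check and may make the decision once per variable, in which case two visits could not fall in different branches. This stands as a limit: the mismatch between visits needs a per-visit decision, which the text allows but does not require. It does not remove the point. The switching rule is written into the protocol, and an SAP that only named a test would still carry it out and still let the data choose the parameter.

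A reader might infer that the planned Day 75 to Day 365 change could be produced by the switch alone. The documents do not support that. Section 4.1.2.1 reads naturally as a difference within each subject, which is one variable with one estimator. Nothing says that one group summary is subtracted from another. The change variable does pass through the same rule, but the artefact belongs to comparisons between tables.

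A reader might also take LI as proof of marked skewness. Its reference percentiles are close to normal, so the two means would nearly agree there. LI after transplant may differ, but the protocol gives no such data.

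Nor should the full gap between the population means (12% at log-SD 0.5, 27% at 0.8) be read as the expected apparent fall. The check selects which samples are compared, so the typical realised fall is smaller. It also sits within ordinary noise: at log-SD 0.5, two arithmetic means with no switch already differ with an SD of about 17–23% on the log scale.

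Finally, these are descriptive secondary summaries in a 10-subject pilot. That bears on how serious the point is, not on whether it is right.

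**Conclusion.** The concern holds in a limited form. The protocol itself makes the reported quantity depend on how 10 or fewer values look, does not tie the choice to the endpoint, and leaves the bootstrap parameter unnamed. If the rule is applied per visit to a skewed measure, the visit summaries can be non-comparable in roughly a fifth to a half of cases, with a median apparent fall of about 3–4% to 20% in the half of switches that are falls. Those rates rest on lognormal data and a Shapiro-Wilk check at 5%, neither of which the protocol states. That the estimated quantity is chosen from the data does not depend on either assumption.

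The primary endpoint is binary and unaffected. For measures close to normal the effect is small (ratio 1.05 at log-SD 0.3). The limit of 10 values follows the synopsis and Sections 4 and 10.4. Section 1.4.2 instead speaks of the "immunosuppressive medication in 20 subjects with long-standing T1D", and that figure needs reconciling.

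**What to change.** Replace the data-driven rule in Section 10.2.2 with one summary and one scale for each continuous endpoint. Set them before the data are seen, use them at every visit whatever a normality check shows, and name the parameter. For example:

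- the mean for measures expected to be near normal;
- a geometric mean, labelled as such, only for skewed measures that are strictly positive;
- the median for measures that can be zero or negative. A HYPO score can be zero, and AIRglu is an incremental area, so it and the disposition index derived from it can be zero or negative. A log scale fails for these.

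For the median, use the narrowest order-statistic interval with at least 95% coverage: 2nd to 9th value at n = 10, 2nd to 8th at n = 9, minimum to maximum at n = 6 to 8. At n = 5 or fewer, which may occur after second or third transplants, report the median and range without a 95% claim. If a bootstrap is kept, state which parameter it estimates.

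Branch mismatch between visits is then zero by construction. The cost is one paragraph and median intervals that are wide, at n = 6 to 8 the whole sample range.

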### **10.3 Patient and Demographic Data**

#### **10.3.1 Baseline Characteristics and Demographics**

Summary descriptive statistics for baseline and demographic characteristics will be provided for the intent-to-treat population. Demographic data will include age, sex, race, ethnicity, sex, height and body weight; these data will be presented in the following manner:

- Continuous data (*i.e.*, age, body weight, and height) will be summarized descriptively by mean, standard deviation, median, and range;
- Categorical data (*i.e.*, sex and race) will be presented as enumerations and percentages.

#### **10.3.2 Medical History**

Medical history will be collected, including the existence of current signs and symptoms and clinical significance for each body system. Numbers and rates of treated subjects with previous history of each condition will be reported.

#### **10.3.3 Use of Medications**

All medications used will be coded using the World Health Organization (WHO) drug dictionary. The number and percentage of subjects receiving concomitant medications or therapies will be presented.

#### **10.3.4 Study Completion**

The percent of subjects who complete the study, losses to follow-up, times to lost to follow-up, and reasons for loss to follow-up (e.g., AEs) will be presented. Statistical presentation of study completion may be further defined in the SAP.

## 10.4 Sample Size and Power Calculations

The purpose of this pilot study is to estimate the true rate of insulin independence at 75 days. The selected sample size is 10 subjects. The point estimate of the true insulin independence rate will be the proportion of the 10 patients that achieve insulin independence. The precision of the estimate depends on the observed number of subjects achieving insulin independence. The following table displays the confidence intervals that would be computed for each possible outcome. If 5 of the 10 subjects achieve insulin independence then the estimated rate will be 50% and a 95% confidence interval will be 0.1871 to 0.8129. That is, we are 95% confident that the true rate is at least 18.71% and no more than 81.29%. The confidence interval rules out any rate less than 18.71% or greater than 81.29%. If 3 patients (30%) achieve insulin independence, then the confidence interval will rule out any rate less than 6.67% or greater than 65.25%.

*Table 5: Confidence Intervals for each possible outcomes*

Number of Subjects insulin Independent at 75 Days	Estimated Rate	Exact 95% Confidence Interval	
		Lower Bound	Upper Bound
0	0	0	0.3085
1	0.1	0.0025	0.445
2	0.2	0.0252	0.5561
3	0.3	0.0667	0.6525
4	0.4	0.1216	0.7376
5	0.5	0.1871	0.8129
6	0.6	0.2624	0.8784
7	0.7	0.3475	0.9333
8	0.8	0.4439	0.9748
9	0.9	0.555	0.9975
10	1	0.6915	1

## **10.5 Reporting Deviations from Original Statistical Plan**

The principal features of the study design and of the plan for statistical analysis of the data are outlined in this protocol and in the subsequent SAP. Any changes in these principal features will require a protocol or an SAP amendment, which would be subject to review by the Steering Committee, the independent DSMB, the study sponsor, and the health authorities. These changes will be described in the final report as appropriate.

## **11. IDENTIFICATION AND ACCESS TO SOURCE DATA**

### **11.1 Identifying Source Data**

The investigator is required to keep accurate records to ensure that the conduct of the study is fully documented (see section 12). The results of all clinical and clinical laboratory evaluations will be maintained in the subject's medical records and the data will be transferred to clinical CRFs.

Safety data will be recorded on CRFs specifically designed for this purpose. All data will be reviewed periodically by the DSMB and IRB. The DSMB and/or the IRB have the authority to withdraw any subjects and/or terminate the study because of safety findings.

### **11.2 Permitting Access to Source Data**

The investigational site participating in this study will maintain the highest degree of confidentiality permitted for the clinical and research information obtained from the subjects and donors in this clinical trial. Medical and research records should be maintained at each site in the strictest confidence. However, as a part of the quality assurance and legal responsibilities of an investigation, the investigational site must permit authorized representatives of the sponsor(s) including pharmaceutical collaborators and their commercial partners, and health authorities to examine (and when required by applicable law, to copy) clinical records for the purpose of quality assurance reviews, audits, and evaluations of the study safety and progress. Unless required by the laws that permit copying of records, only the coded identity associated with documents or with other subject data may be copied (and all personally identifying information must be obscured). Authorized representatives as noted above are bound to maintain the strict confidentiality of medical and research information that is linked to identified individuals. The investigational site will normally be notified before auditing visits occur.

## **12. QUALITY CONTROL AND QUALITY ASSURANCE**

The investigator is required to keep accurate records to ensure that the conduct of the study is fully documented.

The sponsor is responsible for regularly reviewing the conduct of the trial, for verifying adherence to the protocol, and for confirming the completeness, consistency, and accuracy of all documented data.

### **12.1 Data Handling**

The site PI is required to keep accurate records to ensure that the conduct of the study is fully documented, and to ensure that CRFs are completed for all subjects according to study guidelines outlined in the study protocol and the Data System Users Instruction Manual.

Access to the data entry screens will be user ID and password protected. Each user will be provided with a unique personal ID and password. The investigational site participating in this study will maintain the highest degree of confidentiality permitted for the clinical and research information obtained from the subjects in this clinical trial. Medical and research records should be maintained at each site in the strictest confidence. However, as part of the quality assurance and legal responsibilities of an investigation, the investigational site must permit authorized representatives of the sponsor(s) and health authorities to examine (and when required by applicable law, to copy) clinical records for the purpose of quality assurance reviews, audits, and evaluations of the study safety and progress. Unless required by the laws that permit copying of records, only the coded identity associated with documents or with other subject data may be copied (and all personally identifying information must be obscured). Authorized representatives as noted above are bound to maintain the strict confidentiality of medical and research information that is linked to identified individuals. The investigational site will normally be notified before auditing visits occur.

All data will be entered, stored, and managed in a relational database supported by database servers at the DCC. The results of all clinical and laboratory evaluations will be maintained in the subjects' medical records and the data will be transferred from these source documents directly to the electronic study CRFs. In order to maintain security, all data will be encrypted using the Secure Sockets Layer protocol. This protocol allows an encrypted link to be established between the DCC web server and the computer at each center. In addition, the data will be verified by a series of computerized edit checks, and all relevant data queries will be resolved regularly. All discrepancies will be reviewed, and any resulting queries will be resolved with the site personnel and amended in the database.

All changes made to CRFs will be recorded in an electronic audit trail to allow all data changes in the data system to be monitored and maintained in accordance with federal regulations. Once a CRF is entered into the database and the person entering the data indicates that CRF is complete, any change to that data will be entered into the system's audit trail. The audit trail will record the CRF and variable that is changed, the old value, the new value, the date and time the change was made, reason change was made, and the user ID of the person making the change. Once a change is completed, the data system will re-validate all variables on that CRF. The changed CRF will be required to pass all validity and logic consistency checks. If any edit criteria fail, the system will generate appropriate queries. The clinical center coordinator will be asked to resolve the questions before the changes are completed.

The change system will allow certified DCC personnel and certified clinical center coordinators to make changes. Changes can be initiated by DCC monitors, DCC coordinators, and certified site personnel. Site personnel can access only the data for their own center. The system will generate weekly summary listings of all changes made to the database, the person making each change, and the reason for each change. These reports will be carefully reviewed by the DCC coordinator to monitor for unnecessary changes and/or problems with the data system.

